2.0 STUDY OBJECTIVES

2.1 Primary Objective

Assess the incidence of conversion of non-inflamed (TIL/TAL-absent by histopathologic analysis of H&E-stained tissue section from archived metastatic melanoma tumors) to inflamed melanomas following 3 weeks of entinostat monotherapy by performing histopathologic analysis of representative H&E-stained tissue sections from melanoma tumors before treatment and in the end of cycle 1, beginning of cycle 2 (day 22±2 days), immediately before concurrent pembrolizumab-entinostat treatment on day 22 (±2 days) following single-agent entinostat treatment.

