5.0 TREATMENT PLAN

5.1 Schema

Eligible subjects must have histologically confirmed AJCC stage III/IV melanoma of any subtype and sufficient, archived metastatic tumor tissue to confirm absence

of TIL/TAL in representative H&E-stained tumor tissues. Subjects are eligible even if they have received any prior PD-1/PD-L1 pathway inhibitors or any other systemic treatments, including immunotherapies, on condition that they have not received HDACi for their melanoma. They must have recovered from any side effects associated with prior anticancer treatments. Patients will be 'primed' with entinostat, 5mg PO qwk, for 3 weeks. In the end of cycle 1, beginning of cycle 2 (day 22±2 days), immediately before concurrent entinostat-pembrolizumab treatment, they will undergo a mandatory melanoma biopsy after which they will receive up to 4 infusions of standard of care pembrolizumab along with weekly administration of entinostat. Restaging radiographic studies will be performed on week 10 and then every 6 weeks until week 27. Peripheral blood will be collected at baseline; in the end of cycle 1, beginning of cycle 2 (day 22±2 days), immediately before concurrent entinostat-pembrolizumab treatment; on week 10 after 3 infusions (cycles) of pembrolizumab; and at the end of treatment, either at disease progression or week 27, or if intolerable toxicity occurs that requires permanent discontinuation of pembrolizumab and/or entinostat. Subjects will be considered to have completed all trial requirements if:

- (a) Their disease has progressed by RECIST v1.1 criteria within less than 10 weeks from the first dose of entinostat,
- (b) They develop toxicity related to pembrolizumab or entinostat, but still complete sample collection (peripheral blood and tumor tissue) and tumor assessments by at least week 3,
- (c) Complete the entire 27 weeks of combination therapy and study-related assessments without experiencing disease progression by RECIST v1.1 criteria or clinical grounds. Those subjects experiencing clinical benefit after 27 weeks may continue pembrolizumab therapy per standard of care.

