5.2 Treatment Dosage and Administration

Subjects in this trial will be administered entinostat, 5mg PO, once weekly (D1, D8, D15 of a 21-day cycle) starting on day 1 of study treatment. Pembrolizumab, 200 mg will be administered intravenously (IV) every 3 weeks and initiated at cycle 2 after the mandatory research tumor biopsy in the end of cycle 1, beginning of cycle 2 (day 22±2 days). Combination therapy with both agents will continue if subject is receiving clinical benefit from therapy for up to 27 weeks (8 cycles of combination therapy or approximately 6 months). Study therapy will be discontinued for intolerable toxicity, disease progression or for other reasons at the discretion of the investigator.

Agent	Required Premedications; Precautions	Dose	Route	Schedule	Cycle Length
Entinostat	Take on an empty stomach i.e., at least 2 hours after a meal and at least 1 hour before the next meal.	5 mg ³	Oral (PO)	Start on study D1 of cycle 1 and administer once weekly (i.e., D1, D8, D15 of each cycle) for 9 cycles qwk) (±1 day)	Every 21* days
Pembrolizumab	Risk for immune-mediated ¹ and infusion-related ² reactions	200 mg ³	IV; administer over 30 min (range -5, +10 min)	Start on study D22 (± 2 days) of the study (i.e., D1 of cycle 2) and administer every 21 (± 2) days (q3wk) x 8 cycles (i.e., cycles 2-9)	

1. See Section 5.3.2 for management guidelines for immune-mediated AEs.
2. See Section 5.6.1 for management guidelines for infusion-related AEs
3. On days when entinostat is administered on the same day as pembrolizumab, entinostat should be taken before the pembrolizumab infusion.

*Entinostat monotherapy for cycle 1 and combination therapy should be initiated on D1 of cycle 2 and continue until withdrawal for toxicity, withdrawal for patient preference, disease progression or the subject completes 27 weeks of protocol-directed therapy. Entinostat cannot be continued beyond the 27-week duration of study-directed therapy for the trial, irrespective of treatment response.

*Pembrolizumab will be started on D22 of the study (i.e., D1 of cycle 2) and may continue for up to 24 weeks in combination with entinostat (i.e. cycles 2-9). Following completion of the trial therapy at 27 weeks and on condition that there is no disease progression, pembrolizumab can be continued per investigator discretion, as per standard of care guidelines.

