7.4.2 Study Day 22 ± 2 days (D1 of Cycle 2/Week 4)

1. Clinical evaluation: focused history and physical exam,
2. ECOG performance status,
3. 12-lead ECG,
4. Laboratory studies:
 - Hematology
 - Serum Chemistries
 - Collect peripheral blood for isolation of PBMCs (approximately 50 mL)
5. Mandatory Fresh Tumor biopsy (excisional, punch, or CT-guided),
6. Concomitant medication review,
7. Toxicity Assessment,
8. Patient pill diary check,
9. Entinostat administration: 5mg PO to be administered after mandatory biopsy; also dispense two 5-mg pills for administration on D28 and D35,
10. Pembrolizumab administration: 200 mg IV dose; to be administered after mandatory biopsy and after entinostat intake.

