9.1.1 Definitions

Evaluable patients are those who complete all activities by at least day 22, namely: (a) they have received at least one and up to 4 entinostat weekly doses on day 1 and day 8, 15 and 22 (b) they have received the first pembrolizumab infusion on day 22 (± 2 days), and (c) they have completed day 22 (± 2 days) mandatory tumor biopsy. The rationale for this is to answer the primary translational endpoint regarding entinostat-alone immunomodulatory effects in peripheral blood and tumor tissue with sufficient power.

- SAE are events that meet FDA's definition as defined in [section 8.1.4](#) of the protocol irrespective of attribution to study drug(s). Subjects who receive at least one dose of entinostat are evaluable for safety.

- ORR by RECIST 1.1 criteria is the sum of complete response and partial response.

- PFS is measured from the date of enrollment on study to the date of documented progression. The rate of patients who are progression-free will be specifically calculated at 27-weeks (approximately 6 months) from study entry.

- OS is measured from the date of enrollment on study to the recorded date of death. The rate of patients who are alive at 27-week (approximately 6 months) will be specifically calculated for the study.

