9.2 Sample Size, Accrual and Duration of Accrual

Our goal is to enroll at least 10 evaluable patients. The immune-mediated mechanism of action of entinostat alone (primary translational endpoint) will be evaluated on representative H&E-stained tissue sections from tumor tissues collected at baseline and on day 22 by standard pathology analysis. This analysis will be conducted by [name], study pathologist. Density of TIL/TALs in these H&E-stained sections will be scored as a 0, 1+ (non-brisk), 2+ (brisk) ordinal variable¹⁵¹. By definition, upon enrollment if TILs are present based on H&E stained sections, they must be $\leq 1\%$ of the total number of cells in the specimen. A non-inflamed melanoma may have been ‘successfully’ converted to an inflamed melanoma following 21 days of entinostat ‘priming’ if the histopathologic analysis of day 22 melanoma biopsies shows any (i.e. brisk or non-brisk) evidence of TIL/TAL. In other words, we will capture the incidence of conversion as a dichotomous variable, present (i.e. brisk or non-brisk) or absent. Twenty-one days of entinostat ‘priming’ would be considered to have an immunomodulatory effect if at least 3 out of 10 evaluable patients show conversion of their melanomas from ‘non-inflamed’ to ‘inflamed’. This test has a type I error rate of 0.04 if the true rate is 0.08 and power of 83% if the true rate is 0.4.

The secondary endpoint is antitumor response by RECIST 1.1. Given that one of the determinants of response to single-agent PD-1 inhibitors is pre-existing TIL/TAL²⁹, we postulate that patients with metastatic melanoma and zero TIL/TAL will have nearly zero response rate. With 10 patients the exact 95% confidence interval for response rate is (0, 0.31) if 0 responses are observed out of 10 patients, and (0, 0.45) if 1 response is observed out of 10 patients.

Assuming that 20% of patients will not be evaluable due to screen failure, toxicity or rapid disease progression, and another 30% of enrolled patients will not have interpretable tumor biopsies on day 22 due to necrosis, stromal contamination or overall low quality, the total number of enrolled patients should be set to 14.

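### Section 9.1.1(b) makes evaluability for the entinostat-alone conversion endpoint depend on a pembrolizumab infusion given after the deciding biopsy

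*Combined protocol and SAP*

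**What the plan says.** Section 2.1 sets the primary objective as conversion after three weeks of entinostat monotherapy, with the on-treatment biopsy taken "immediately before concurrent pembrolizumab-entinostat treatment on day 22" (±2 days). Section 5.2 says pembrolizumab is "initiated at cycle 2 after the mandatory research tumor biopsy", and the day-22 visit list in 7.4.2 has it "to be administered after mandatory biopsy and after entinostat intake".

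Section 9.1.1 defines evaluable patients by three conditions joined by 'and': (a) at least one entinostat dose; (b) "they have received the first pembrolizumab infusion on day 22" (±2 days); (c) a completed day-22 (±2 days) biopsy. It justifies the definition as follows: "mandatory tumor biopsy. The rationale for this is to answer the primary translational endpoint regarding entinostat-alone immunomodulatory effects".

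Section 9.2 applies the decision rule to evaluable patients: at least 3 conversions out of 10, with type I error 0.04 at a true rate of 0.08 and power 83% at 0.4. The same section plans for losses: "Assuming that 20% of patients will not be evaluable due to screen failure, toxicity or rapid disease progression", plus a further 30% with biopsies that cannot be interpreted.

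**The concern.** Condition (b) is met or missed after the endpoint has been measured. It cannot change what the biopsy shows, and an entinostat-alone question gives no reason to require it. A patient can have a complete, readable day-22 biopsy and still leave the primary denominator because pembrolizumab was not started in the window. No section returns such a patient to the conversion analysis.

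Two things are at stake. First, if missing the infusion is related to conversion, the retained patients are a selected group, and the error rates in 9.2 do not apply to the population the objective describes. Second, readable primary-endpoint biopsies are discarded in a trial that aims for only 10. Meanwhile, condition (c) asks for a completed biopsy, not a scorable one. The definition therefore requires something the endpoint does not need and omits something it does.

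**Working it through.** **1. Order of events.** Entinostat on days 1, 8 and 15; biopsy on day 22 ±2, that is, days 20 to 24; then entinostat and pembrolizumab (5.2, 7.4.2). The infusion has the same window, so a biopsy on day 24 leaves no later day on which (b) can still be met.

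**2. Can (b) fail after a valid biopsy?** Yes. For events in the immune-related table, 5.3.2 holds both drugs whichever drug is blamed. That table includes diarrhea/colitis and AST/ALT elevation, which 5.3.3 names among the toxicities the two drugs share. Section 9.2 itself lists toxicity and rapid progression as causes of non-evaluability.

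**3. The plan's own figures (exact binomial, n = 10, success if X ≥ 3).**
- Type I error at 0.08: 1 − [0.92^10 + 10(0.08)(0.92^9) + 45(0.08²)(0.92^8)] = 1 − (0.4344 + 0.3777 + 0.1478) = 0.0401.
- Power at 0.40: 1 − [0.6^10 + 10(0.4)(0.6^9) + 45(0.4²)(0.6^8)] = 1 − (0.0060 + 0.0403 + 0.1209) = 0.8327.

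Both agree with 9.2.

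**4. Effect of selection.** Let p be the true conversion rate among all patients with a readable biopsy, m the share failing (b), and d the conversion rate among those dropped. The rate among those retained is r = (p − m·d)/(1 − m). The rule is then evaluated as P(X ≥ 3) with n = 10 and rate r. The documents give neither m nor d, so both are assumptions. I take m = 5%, 10% and 20%. The 20% in 9.2 is only a loose guide, because it also covers screen failures and patients who never reach a biopsy.

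| Assumption about dropped patients | m = 5% | m = 10% | m = 20% |
|---|---|---|---|
| p = 0.08, d = 0: r | 0.0842 | 0.0889 | 0.1000 |
| Type I error | 0.046 | 0.052 | 0.070 |
| p = 0.08, d = 0.04 (half): r | 0.0821 | 0.0844 | 0.0900 |
| Type I error | 0.043 | 0.046 | 0.054 |
| p = 0.08, d = 0.08 (same): type I error | 0.040 | 0.040 | 0.040 |
| p = 0.08, d = 0.16 (twice): type I error | 0.035 | 0.030 | 0.019 |
| p = 0.40, d = 0.80 (twice): r | 0.3789 | 0.3556 | 0.3000 |
| Power | 0.796 | 0.750 | 0.617 |

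**5. Effect of loss without selection.** If 1 or 2 of 10 readable biopsies are lost and not replaced, and the cut-off stays at 3, power at 0.40 is 0.768 (n = 9) or 0.685 (n = 8). Type I error falls to 0.030 or 0.021.

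**6. What happens if (b) is removed.** With exactly 10 scorable biopsies, the rule keeps 0.040 and 0.833. With more than 10 it does not:

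| Rule | Type I error at 0.08 | Power at 0.40 |
|---|---|---|
| ≥3 of 11 | 0.052 | 0.881 |
| ≥3 of 12 | 0.065 | 0.917 |
| ≥4 of 12 | 0.012 | 0.775 |

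Removing (b) without fixing the denominator would therefore add about as much type I error as the all-non-converter case in step 4.

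**The case against.** The route out under (b) may be narrow. Biopsy and infusion belong to the same visit. No imaging is scheduled at day 22; the first on-treatment scan is at week 10, so progression at that point would have to be found clinically or on an unscheduled scan. The entinostat toxicity tables in 5.3.1 modify entinostat, not pembrolizumab. The number affected could be small or zero, and 1.1 calls the trial exploratory. Section 9.2 also aims for at least 10 evaluable patients, so replacement would limit the power loss. All of this stands. It bears on size, not on whether (b) belongs in the definition.

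A reader might infer more than the documents support, in four places:
- Condition (a) mentions the day-22 entinostat dose, which follows the biopsy. But (a) is met by a single dose, so that mention excludes no one.
- The delay allowances in 5.3 begin at cycle 3. They concern side effects of pembrolizumab, which cannot occur before the first infusion, so their silence about cycle 2 shows nothing.
- Section 5.1(b) may look like a rival analysis set: "They develop toxicity related to pembrolizumab or entinostat, but still complete sample collection (peripheral blood and tumor tissue" and so on, with tumor assessments also required. It defines when a subject has finished the trial's requirements, not who is evaluable. Its wording should be made consistent, but it does not contradict 9.1.1.
- One might conclude that the conversion rate will be inflated. That needs dropped patients to convert less often than the rest, which is plausible for rapid progressors but not shown.

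**Conclusion.** The point holds as a fault in the definition. Condition (b) ties the primary denominator to an event that comes after the measurement and cannot affect it, and the rationale given in 9.1.1 does not support it. The error rate and power in 9.2 are correct for 10 evaluable patients; the fault is in who counts as evaluable.

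The size rests entirely on assumed values of m and d. Over the range shown, type I error moves from 0.040 to at most 0.070 when no dropped patient is a converter and does not move when conversion is unrelated to being dropped. Power falls to as low as 0.617 when dropped patients convert at twice the overall rate. The direction cannot be determined from the documents. The correction is worth making because it removes a possible selection effect and keeps valid data, and it needs only a change of text.

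**What to change.** - **9.1.1:** define a conversion-evaluable set as patients with at least one entinostat dose before the biopsy and a day-22 (±2 days) biopsy that can be scored. Keep receipt of pembrolizumab only as a condition for the combination-treated summaries (response and PFS).
- **9.2:** either apply the 3-of-10 rule to the first 10 conversion-evaluable patients, or state the cut-off and its error rates for each n above 10, using the figures in the last table of the working.
- **9.2 and 9.3:** report the combination response rate with its own denominator.
- **5.1(b):** make the completion wording consistent with the new definition.

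The change needs no new procedure or data, since the biopsies are already taken. Its one real cost is that patients without pembrolizumab may fill some of the 10 conversion places, so the response denominator may drop below 10 unless more are enrolled. With 0 responses the exact 95% upper limit is 1 − 0.025^(1/n): 0.308 for n = 10 (the plan's 0.31) and 0.336 for n = 9.

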2.2 Secondary Objectives

- 2.2.1 Assess antitumor response rate to the pembrolizumab-entinostat combination in patients with ‘non-inflamed’ melanomas (TIL/TAL-absent by histopathologic analysis of H&E-stained tissue section from archived metastatic melanoma tumors) irrespective of prior PD-1/PD-L1 inhibitor treatment status after 3 cycles (9 weeks) of study treatment by RECIST v1.1 criteria.
- 2.2.2 Assess the 6-month (i.e. 27 weeks) progression-free survival (PFS) rate in patients with ‘non-inflamed’ (TIL/TAL-absent), irrespective of prior PD-1/PD-L1 inhibitor treatment status treated with the pembrolizumab-entinostat combination by RECIST v1.1 criteria.
- 2.2.3 Assess toxicity of the concurrent pembrolizumab-entinostat combination based on NCI-CTCAE v.5.0.

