3.2 Secondary Endpoints

- 3.2.1 The ORR (CR + PR) at 10 weeks will assessed based on RECIST v1.1 criteria.
- 3.2.2 PFS rate at approximately 6 months (i.e. 27 weeks) is defined as the time from day 1 of treatment until disease progression or death status measured 6 months after initiating study treatment. Progression events will be defined per RECIST v1.1 criteria.
- 3.2.3 The toxicity will be assessed based on the NCI CTCAE v 5.0 criteria. For example, the incidence of AEs that occur in subjects enroll who receive at least one dose of therapy.

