6.3.6 Disease Assessment

This following test should be performed for assessment of melanoma disease.

6.3.6.1 Computed tomography (CT) of the whole body i.e., neck (if applicable), chest, abdomen, pelvis with IV contrast (or abdominal/pelvis MRI if allergy to IV contrast)

Baseline (screening) disease assessment should be obtained within 21 days of initiating study treatment. During the study, scans will be repeated as outlined in the Time and Events table in section 7.1 (i.e., at the end of week 10[D1 of cycle 4 or Study day 64/Wk10], end of week 15 [D1 of cycle 6 i.e., Study day 106/Wk16], end of week 21 [D1 of cycle 8 or Study day 148/Wk22], and end of week 27). Scans obtained during study treatment may be performed within ± 7 days of the scheduled study visit.

6.3.6.2 *Magnetic Resonance Imaging (MRI) of the brain*

MRI of the brain must be obtained at baseline (screening) and at end of treatment (i.e., at time of disease progression or at week 27); on any other visit **only if clinically indicated**, as per standard of care. If brain MRI is not feasible, patient can have a CT scan with IV contrast.

6.3.7 **Pre-Screening Pathology Assessment Period (pre-screening only)**

Given the limited 21-day screening period, and the requirement for absent TIL/TAL in melanoma tissues, archival metastatic tissue (locoregional, distant metastatic) can be requested and assessed before study enrollment (pre-screening). There is not an official pre-screening period given that [name], study's pathologist, is UNC's sole melanoma pathologist and routinely signs off his pathology reports, either from outside consultation slides or from in-house cases, along with a report about the presence of absence of tumor-infiltrating/-associated lymphocytes. If not available already, representative tumor sections from archived tumor blocks will be stained with H&E and will be assessed by [name], study pathologist, for assessment of quality using these criteria: (1) the tumor surface area must be at least 1cm² (which can be from a combination of metastatic blocks if necessary), (2) no more than 20% of necrosis, (3) the ratio of viable tumor cells to tumor-associated stroma should be at least 60/40, and (4) if TILs are present based on H&E stained sections, they must be $\leq 1\%$ of the total number of cells in the specimen; the amount of tissue should be ≥ 1 cm².

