7.5 Post Treatment Follow-Up Assessments

7.5.1 End of Study Treatment Visit (Week 28, or earlier if disease progression, intolerable toxicity, patient withdraw) within + 7 days of stopping study treatment

1. Clinical evaluation: focused history and physical exam,
2. ECOG performance status,
3. 12-lead ECG
4. Laboratory studies:
 - Hematology
 - Serum Chemistries
 - Endocrine panel: include fT4/TSH only
5. Disease assessment (chest, abdomen and pelvis; neck if applicable),
6. Collect peripheral blood for isolation of PBMCs and plasma (approximately 50 mL)
7. Brain MRI (if applicable),
8. Concomitant medication review,
9. Toxicity Assessment.

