9.3 Data Analysis Plans

Tumor response and AE of the entinostat-pembrolizumab combination will be tabulated and 95% confidence interval will be computed. PFS and OS will be estimated using Kaplan Meier method.

[REDACTED] The tumor imaging at baseline and on day 22, the peripheral blood assessment, and the baseline assessments for targeted mutation panel sequencing (FoundationOne®, or other targeted panel sequencing commercially available panel) are secondary correlative endpoints.

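### Sections 9.1.1 and 3.2.2 define PFS differently; read literally, 9.1.1 leaves out deaths without documented progression, so its 27-week rate can only be equal or higher

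*Combined protocol and SAP*

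**What the plan says.** The 27-week PFS rate is a secondary endpoint, and two current sections define it.

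- Section 3.2.2 (endpoints): the rate is "defined as the time from day 1 of treatment until disease progression or death status measured 6 months after initiating study treatment". The clock starts with treatment, and death is an event.
- Section 9.1.1 (statistical definitions): "PFS is measured from the date of enrollment on study to the date of documented progression", with the rate "specifically calculated at 27-weeks (approximately 6 months) from study entry". The clock starts at enrolment, and only documented progression is named as an event. The next item in the same list defines OS and does name the date of death.

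Two other places touch the endpoint without settling the matter. Objective 2.2.2 reads "Assess the 6-month (i.e. 27 weeks) progression-free survival (PFS) rate in patients with" non-inflamed disease and gives neither a start date nor a death rule. Section 9.3 says "PFS and OS will be estimated using Kaplan Meier method"; the text directly after that is redacted.

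On timing, Section 6.3.6.1 places the first on-treatment scan "at the end of week 10[D1 of cycle 4 or Study day 64/Wk10" and the last at the end of week 27. Sections 5.9 and 7.5.2 require the date of death to be recorded during follow-up.

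**The concern.** The two definitions differ on the event and on the time origin. Two analysts who each follow one section faithfully could report different 27-week PFS rates from the same data.

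The difference in event has a known direction. A patient who dies without documented progression fails under Section 3.2.2. Under a literal reading of Section 9.1.1 the same patient is either censored at death or left among the progression-free. Such a death is possible by design, because no on-treatment scan is scheduled before study day 64.

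The origin matters too. Enrolment cannot be later than the first day of treatment, so 27 weeks from enrolment is the same point in treatment time or an earlier one.

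With 10 to 14 patients, one patient's classification is visible in the reported rate. If the conflict is left open until analysis, the choice may be made with the data in view.

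**Working it through.** **1. Is there a plan figure to reproduce?** Not for PFS: the documents give no assumed rate, target or power for it. The only design figures in Section 9.2 that could be checked nearby belong to the primary endpoint. The rule of at least 3 conversions in 10 gives an exact binomial type I error of 0.0401 at a true rate of 0.08 and power of 0.8327 at 0.4, matching the stated 0.04 and 83%. Nothing below alters them.

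**2. Inputs.** No readable passage states the PFS analysis population, so n is an assumption: 10 (minimum evaluable, Section 9.2), 12 (maximum evaluable, Section 1.1) or 14 (enrolled, Section 9.2). The documents give no event counts. The illustration assumes one death without documented progression before week 27, a true rate of 50% and no other censoring.

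**3. Formula.** Let k patients progress and one die without documented progression by week 27.

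- Death counted (Section 3.2.2): S = (n − k − 1)/n.
- Death censored after j of the k progressions (Section 9.1.1, literal, Kaplan-Meier): S′ = S × (n − j)/(n − j − 1).
- Shift: S′ − S = (n − k − 1)/[n(n − j − 1)]. This is never negative, and because j ≤ k it is at most 1/n.

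**4. Results.**

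| n | k | S (death counted) | S′, death before all progressions | S′, death after all progressions | Maximum shift 1/n |
|---|---|---|---|---|---|
| 10 | 4 | 50% | 5/9 = 55.6% | 6/10 = 60.0% | 10.0 points |
| 12 | 5 | 50% | 6/11 = 54.5% | 7/12 = 58.3% | 8.3 points |
| 14 | 6 | 50% | 7/13 = 53.8% | 8/14 = 57.1% | 7.1 points |

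The 1/n figure is also what a simple proportion would give if the dead patient were counted as progression-free. With two such deaths, n = 10 and four progressions, 40% becomes 50% to 60%. With no such death the shift is zero.

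**5. Time origin.** Section 7.1 allows screening assessments up to 21 days before treatment. The enrolment date is not defined; if it falls within screening (assumption), the gap g is 0 to about 21 days. Since 27 × 7 = 189 days, the enrolment-based landmark lies 189 − g days after C1D1, that is, 168 to 189 days. The effect on the rate cannot be put in points, because no event-time distribution is given.

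**6. Final scan.** Section 6.3.6.1 pairs the end of week 15 with study day 106 (105 days after C1D1) and the end of week 21 with study day 148 (147 days after). On that pattern the end of week 27 is 189 days after C1D1, or study day 190, the first day of week 28. The windows allow up to 7 days later, so the scan can fall as late as 189 + 7 = 196 days after C1D1. With an enrolment origin and g ≥ 1, even an on-time final scan lies beyond 189 days from enrolment.

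**The case against.** The strongest reply is that PFS conventionally includes death, that Section 3.2.2 says so, and that Section 9.1.1 is shorthand. Section 3.2.2 does show the intention. But Section 9.1.1 is where an analyst looks for definitions, it names death under OS and not under PFS, and it also changes the start date, which shorthand does not explain. The redacted text in Section 9.3 may hold a censoring rule, but that would still leave two readable definitions in conflict.

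A second reply is that the effect is small beside the imprecision: the exact 95% interval for 5 of 10 is about 19% to 81%. The study is exploratory and PFS has no test. This stands, and it limits the importance of the point.

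Three stronger readings are tempting, and the documents do not support them.

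- A reader might infer that the final assessment carries conflicting labels, since one section has "and end of week 27). Scans obtained during study treatment may be performed within" a window and another has "End of Study Treatment Visit (Week 28, or earlier if disease progression". By the pattern in Section 6.3.6.1 (end of week 15 is Wk16, end of week 21 is Wk22) the two labels largely agree; only the week 10 entry breaks the pattern.
- A reader might infer from Section 9.2 that early deaths are expected, because it allows for rapid disease progression. Documented progression is an event under both definitions, so this is no evidence of deaths without it. Section 9.2 also treats those patients as non-evaluable.
- A reader might take 10.0, 8.3 or 7.1 points as the expected bias. Under the Kaplan-Meier method that the plan names, they are upper bounds for one death.

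The choice of n is also open to challenge. The figure of 14 allows for screen failures, who would have no C1D1, and a patient who dies before the day-22 procedures is not evaluable under Section 9.1.1.

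**Conclusion.** The conflict is real and sits in current text. Sections 3.2.2 and 9.1.1 disagree on when PFS starts and on whether death ends it, and no readable passage gives precedence.

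On the death rule, a literal Section 9.1.1 rate can only be equal to or above the Section 3.2.2 rate. In the illustration, one uncounted death lifts a true 50% by about 4 to 10 points, depending on n and on when the death occurs. This rests on the assumed population, the single assumed death and the absence of other censoring; no death rate is given. The origin difference of 0 to about 21 days rests on the assumption that enrolment falls within screening. It can only move the landmark earlier in treatment time.

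The primary conversion endpoint and its decision rule are untouched. This should be corrected before analysis, but it does not threaten the study's main conclusion.

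**What to change.** Replace the PFS text in Section 9.1.1 with: *PFS is the time from C1D1 to the first of RECIST 1.1 progression or death from any cause; patients without an event are censored at their last disease assessment.* Calculate the 27-week rate from C1D1. This adopts the start and event already in Section 3.2.2 and adds a censoring rule. If the redacted part of Section 9.3 already contains one, make the two agree.

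A minor related addition: the final scheduled scan may, within its window (Sections 6.3.6.1, 7.1 and 7.5.1), fall a few days after 27 weeks from C1D1. State that progression found at that scan counts in the 27-week rate.

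The cost is wording only. Death dates are already collected under Sections 5.9 and 7.5.2, and no visit, scan or sample size changes. The reported PFS rate may be lower than under a literal Section 9.1.1 if a patient dies without documented progression.
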